1.1 TRIAL SUMMARY

Abbreviated Title	Pembrolizumab and Doxorubicin
Trial Phase	Phase I/II
Clinical Indication	Sarcoma
Trial Type	Single arm, open-label
Type of control	Historical
Route of administration	IV
Trial Blinding	None
Treatment Groups	Low and high dose doxorubicin/ phase I and phase II expansion
Number of trial subjects	maximum 47 (44 expected)
Estimated enrollment period	24 months
Estimated duration of trial	48 months
Duration of Participation	48 months

1.2 Table of contents:

1. Title

- 1.1 Trial Summary
- 1.2 Table of contents
- 1.3 Commonly Used Abbreviations

2. Trial Design

- 2.1 Introduction
- 2.2 Dosing Schedule
- 2.3 Management of Normal Doxorubicin Toxicity
- 2.4 Assessment of Response
- 2.5 Phase I Dose Escalation
- 2.6 Phase II Extension
- 2.7 Trial Diagram

3. Objectives

- 3.1 Primary Objectives and Hypothesis
- 3.2 Secondary Objectives and Hypothesis
- 3.3 Exploratory Objectives

4. Background and Rationale

- 4.1 Background
- 4.2 Rationale

5. Methodology

- 5.1 Entry Criteria
- 5.2 Trial Treatments
- 5.3 Concomitant Medications/Vaccinations (allowed & prohibited)

- 5.4 Rescue Medications & Supportive Care related to Pembrolizumab
- 5.5 Diet/Activity/Other Considerations
- 5.6 Subject Withdrawal/Discontinuation Criteria
- 5.7 Subject Replacement Strategy
- 5.8 Criteria for Early Trial Termination

- 6. Trial Flow Chart

- 7. Trial Procedures
 - 7.1 Trial Procedures
 - 7.2 Assessing and Recording Adverse Events
 - 7.3 Analysis of Biopsy Specimen

- 8. Statistical Analysis and Plan
 - 8.1 Statistical Analysis and Plan Summary
 - 8.2 Statistical Analysis Plan

- 9. Labeling, Packaging, Storage and Return of Clinical Supplies
 - 9.1 Investigational Product
 - 9.2 Packaging and Labeling Information
 - 9.3 Clinical Supplies Disclosure
 - 9.4 Storage and Handling Responsibilities
 - 9.5 Returns and Reconciliation

- 10. Administrative and Regulatory Details
 - 10.1 Institutional Review Board
 - 10.2 Consent
 - 10.3 Termination of Study
 - 10.4 Compliance with Trial Registration and Results Posting Requirements

10.5 Response Evaluation Criteria in Solid Tumors (RECIST) 1.1 Criteria for Evaluating Response in Solid Tumors

Appendix A: Data Safety Monitoring Board Charter Data Safety Monitoring Board Charter

Appendix B: ECOG Performance Status

Appendix C: Literature Cited

1.3 Commonly Used Abbreviations:

AE	Adverse Event
APC	Antigen Presenting Cell
APP	Advanced Practice Provider (Nurse practitioners or physician assistants)
BMP	Basic Metabolic Panel
CBC	Complete Blood Count
CMP	Complete Metabolic Panel
CR	Complete Response
CRF	Case Report Forms
CTCAE	Common Terminology Criteria for Adverse Events
CTL	Cytotoxic T Lymphocyte
DLT	Dose Limiting Toxicity
DSMB	Data Safety Monitoring Board
ECI	Events of Clinical Interest
ECOG	Eastern Cooperative Oncology Group
IB	Investigator Brochure
IV	Intravenous
mAb	Monoclonal Antibody
MHC	Major Histocompatibility Complex
OS	Overall Survival
OTC	Over the Counter
PD-1	Programed Death Receptor 1
PD-L1 & 2	Program Death Receptor Ligands 1 & 2
PFS	Progression-free Survival

RECIST	Response Evaluation Criteria in Solid Tumors
RR	Response Rate
SAE	Serious Adverse Event
SD	Stable Disease
SBRT	Stereotactic Body Radiation Therapy
STS	Soft Tissue Sarcoma
TSH	Thyroid Stimulating Hormone
Treg	Regulatory T cell

2.0 TRIAL DESIGN

2.1 Introduction

This is a Phase I/II, non-randomized, open-label, interventional study of Pembrolizumab combined with doxorubicin for patients with advanced sarcoma. Most patients will receive this as front line therapy. As a rule, the trial is generally inclusive for most sarcoma subtypes. However, it excludes patients with prior anthracycline treatment. Patients with Ewings Sarcoma, Osteosarcoma, and some Rhabdomyosarcomas are excluded as these histologic sarcoma subtypes have well-established, evidence-based treatment paradigms combining anthracyclines with other chemotherapy.

The Phase I stage will evaluate two dose levels of doxorubicin (45 and 75 mg/m²) combined with Pembrolizumab. The 75 mg/m² doxorubicin dose is widely considered standard of care for sarcoma, as is being used as the “control” arm for recent and on-going phase III trials (NCT02451943) (Judson, Verweij et al. 2014). All patients will receive Pembrolizumab at the flat dose of 200 mg given intravenously every 3 weeks. Unless serious adverse events are observed, the Phase II expansion will combine the 75 mg/m² dose of doxorubicin with Pembrolizumab.

The phase II portion will use a two stage design treating an initial 20 patients with the combination of Doxorubicin and Pembrolizumab. If two or more objective responses are seen (either complete or partial responses), an additional 15 patients will be treated for a total of 35 patients. In summary, we expect that 44 patients will be treated on the trial (9 in the phase I portion and 35 on the phase II portion). If an additional 3 patients needed to be treated in the initial phase I cohort this could potentially increase to a maximum enrollment of 47.

2.2 Dosing Schedule

In order to “prime” the immune system prior to combination therapy, patients will receive one cycle of Pembrolizumab as a single agent before starting the combination of doxorubicin and Pembrolizumab. Patients will receive a maximum of 6 cycles of doxorubicin. After this, patients with clinical benefit may continue on study with single agent Pembrolizumab.

Pembrolizumab has been given q2 weeks and q3 weeks and the optimal schedule is unclear. However, it is approved by the FDA for use every 3 weeks, and this dosing will also minimize the necessary infusion center visits. Patients will receive Pembrolizumab and doxorubicin sequentially at the same infusion center visit. Doxorubicin will be given first.

Patients with SD, PR or CR may continue to take Pembrolizumab for 2 years (and no more than 35 cycles). After this, they must discontinue Pembrolizumab. If the patient had been responding prior to discontinuation and they immediately progress 8-12 weeks after discontinuation, they may then resume pembrolizumab for one year or until progression.

2.3 Management of Normal Doxorubicin Toxicity and use of Growth Factors

Dosing will be every 3 weeks as is standard of care when doxorubicin is used as a single agent. There are no restrictions any other anti-emetics (NK1 or 5HT3 inhibitors) however, steroids are occasionally used as antiemetics for doxorubicin but are not recommended for patients on this trial as they may interfere with the efficacy of Pembrolizumab.

In general, supportive care will be given according to standard practice. No serious toxicities have been observed to date when Pembrolizumab has been combined with filgastrim and peg-filgastrim so these medications will be generally be allowed to support patients receiving doxorubicin. However, during the first cycle combining doxorubicin with Pembrolizumab (cycle 2) while in the phase I dose escalation portion of the trial, no growth factor will be given. This will allow a simplified look at the safety of the Pembrolizumab and doxorubicin combination.

Patients on single agent doxorubicin sometimes have dose delays secondary to toxicity. Dose delays up to 3 weeks for toxicity not otherwise outlined in section 5.2 will be permitted with PI approval. Lab abnormalities may also necessitate delay in doxorubicin. Detailed information about delays and dose reductions for patients on doxorubicin is given in **section 5.2**. Should either drug be delayed for any reason, the other drug may be given at the discretion of the treating physician in order to minimize infusion center appointments for patients and focus study on the combination.

If a toxicity is clearly attributable to only one drug, the other may be continued per protocol.

2.4 Assessment of Response

Response assessment will be based on RECIST 1.1. Patients with clinical benefit (SD, PR, CR) after 6 cycles of doxorubicin will continue on single agent Pembrolizumab until confirmed progression RECIST, severe toxicity (see **Section 5**), or 2 years of therapy whichever comes first. Patients who receive a CR will be treated until they have had at least 24 weeks of treatment and have been treated for at least 2 cycles after their CR was declared. Patients who are able to be brought to a CR surgically should be treated just as if they had a CR in response to the medication. Patients confirmed to have a CR who have been taken off treatment will continued to be monitored radiographically every 12 weeks. Upon relapse they can be re-treated with Pembrolizumab for up to one year.

While, all patients will start therapy with unresectable/metastatic disease, it is possible that a responding patient becomes surgically resectable so that they have no evidence of disease. These patients may undergo surgery and afterwards should be followed as if they had a CR, with the rules regarding progression and restarting treatment.

Patients will have their first post-treatment scan after 3 cycles of doxorubicin, prior to receiving their fourth cycle of doxorubicin. Patients with PR or SD will have their second post treatment scan 3-6 weeks after their last (sixth) cycle of doxorubicin. Responses will be determined by RECIST 1.1. After 6 cycles of doxorubicin have been completed and Pembrolizumab is being given as a single agent, scans will be performed every 12 weeks (+/- 1 week) until progression.

Subjects with an *unconfirmed* progression of disease may discontinue but will be encouraged to continue trial treatment until progression is confirmed following two additional cycles of therapy or until disease progression becomes symptomatic. However, subjects may only receive study treatment while waiting for confirmation of PD if the following criteria are met:

- No decline in ECOG performance status
- Absence of rapid progression of disease
- Absence of progressive tumor at critical anatomical sites (e.g. cord compression) requiring urgent alternative medical intervention

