5.2.1.3 Dose Modification of Doxorubicin

Doxorubicin is a cytotoxic chemotherapy that has a well-defined safety profile and will be given as per the standard of care. Doxorubicin will not be given while a patient's ANC is < 1000 cells/m³ or if the platelet count is <75,000 cells/m³. When necessary, the next treatment cycle should be delayed until these counts have recovered to these levels. Transfusions of red blood cells and platelets are permitted as clinically indicated. If a patient has a grade 3 febrile neutropenia, doxorubicin should be reduced to approximately 75% of the previous dose (first to 60mg/m² then to 45 mg/m²). Dose reductions of doxorubicin are also required for patients having Grade 4 neutropenia lasting more than 1 week. For patients with grade 3 febrile neutropenia or grade 4 neutropenia without fever lasting less than a week, dose reduction may be made at the discretion of the treating physician. Patients with grade 3 fatigue and/or malaise, may have one dose reduction at the discretion of their treating physician.

Patients may not have more than 2 dose reductions of doxorubicin, and must come off doxorubicin should they continue to have prolonged cytopenias (>21 days) after their second dose reduction. If these patients are responding they may stay on Pembrolizumab as a single agent until progression.

LFT abnormalities may also necessitate a dose reduction. For a bilirubin 1.2-1.5, dose reduction may be made at the discretion of the treating clinician. For bilirubin 1.5 -3, 50% dose reduction. For bilirubin 3.0-5.0, give no more than 25% of the prior dose and consider delaying the next cycle.

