The End of Treatment and Follow-up visit procedures are listed in Section 6 (Protocol Flow Chart) and Section 7.1.5 (Visit Requirements). After the end of treatment, each subject will be followed for 30 days for adverse event monitoring (serious adverse events will be collected for 30 days after the end of treatment as described in Section 7.2.3.1). Subjects who discontinue for reasons other than progressive disease will have post-treatment follow-up for disease status until disease progression, initiating a non-study cancer treatment, withdrawing consent or becoming lost to follow-up. After documented disease progression each subject will be followed by telephone for overall survival until death, withdrawal of consent, or the end of the study, whichever occurs first.

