Pregnancy Test – Urine or Serum (in appropriate study subjects)	X	X	X	X	X	X	X	X	X	X	X	X	X	X	
PT/INR and aPTT	X														
CBC with Differential	X	X	X	X	X	X	X	X	X	X	X	X	X	X	
Comprehensive Serum Chem Panel	X	X	X	X	X	X	X	X	X	X	X	X	X	X	
Urinalysis	X														

Trial Period:	Screening	Pembro Only	Doxorubicin/Pembrolizumab Combination							Pembrolizumab Only (repeat)				End of Treatment	
Treatment Cycle/Title:	Screening	1	2	3	4	5	6	7	8	9	10	11	At time of Discon	30 days post discon	
Scheduling Window (Days):	see section 7.1.5	± 3	± 3	± 3	± 3	± 3	± 3	± 3	± 3	± 3	± 3	± 3	± 7	± 7	
T3, FT4 and TSH	X	X	X	X	X	X	X	X	X	X	X	X	X	X	
Tumor Imaging ¹	X			X					X						
Archival Tissue Collection (slides)	X														
Correlative Studies Blood Collection	X	X	X			X			X				X		

1: Tumor imaging may be performed with a +/- 1-week window. Scans will take place per the schedule even if there are treatment delays.

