7.1.4 Other Procedures

7.1.4.1 Withdrawal/Discontinuation

When a subject discontinues/withdraws prior to trial completion, all applicable activities scheduled for the final trial visit should be performed at the time of discontinuation. Any adverse events, which are present at the time of discontinuation/withdrawal, should be followed in accordance with the safety requirements outlined in Section 7.2 - Assessing and Recording Adverse Events. Subjects who a) attain a CR or b) complete 24 months of treatment with pembrolizumab may discontinue treatment with the option of restarting treatment if they meet the criteria specified in Section 7.1.5.5. After discontinuing treatment following assessment of CR, these subjects should return to the site for a Safety Follow-up Visit (described in Section 7.1.5.3.1) and then proceed to the Follow-Up Period of the study (described in Section 7.1.5.4).

A subject will be considered withdrawn and no longer followed if they enroll onto hospice care.

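### Scans are tied to doxorubicin cycles completed, and disease follow-up after early stopping has no imaging interval (except in complete response), so assessment depends on toxicity and ORR can be biased upward through replacement

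*Combined protocol and SAP*

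**What the plan says.** **On treatment (2.4).** Three triggers are given, and each counts doxorubicin:
- First scan: "Patients will have their first post-treatment scan after 3 cycles of doxorubicin, prior to receiving their fourth cycle of doxorubicin".
- Second scan: "Patients with PR or SD will have their second post treatment scan 3-6 weeks after their last (sixth) cycle of doxorubicin".
- Later scans: "After 6 cycles of doxorubicin have been completed and Pembrolizumab is being given as a single agent, scans will be performed every 12 weeks", with a window of one week either way.

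**Flow chart (6.1).** The Tumor Imaging row has no mark in the discontinuation column or the 30-day column. Its footnote reads "Scans will take place per the schedule even if there are treatment delays"; it does not mention discontinuation.

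**One drug stopped.** Sections 2.3 and 5.2.1.1 let the other drug continue when a toxicity is clearly due to only one of them.

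**All treatment stopped.** Section 7.1.4.1 says "all applicable activities scheduled for the final trial visit should be performed at the time of discontinuation". Section 5.6 adds: "Subjects who discontinue for reasons other than progressive disease will have post-treatment follow-up for disease status until disease progression", or until new cancer treatment, withdrawal of consent or loss to follow-up. It gives no interval. Section 2.4 gives one off treatment for complete responders only: "Patients confirmed to have a CR who have been taken off treatment will continued to be monitored radiographically every 12 weeks". Section 7.1.4.1 refers to 7.1.5.4 for the follow-up period, but Section 7.1.5 ends with survival follow-up, and 7.2 comes next.

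**Evaluability and the primary test.** Section 5.7 plans for up to 35 phase II patients evaluable for response and replaces those who are not. Section 8.2 tests an ORR of 15% against 35% at one-sided 0.05 with 85% power: 20 patients, then 15 more if at least 2 respond, with success at 10 or more responses of 35.

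**The concern.** Early stopping is foreseen: the dose-limiting toxicity definition in 2.5 includes events that end either drug. If the scan schedule advances only as doxorubicin is given, toxicity decides whether and when a patient is assessed.

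Three results are exposed:
- **ORR (phase II primary).** A patient with no post-baseline scan has no documented response. Under 5.7 that patient may be replaced by someone who tolerated treatment long enough to be scanned.
- **PFS.** For early stoppers, the progression date rests on whenever imaging happens to be done.
- **Duration of response.** The same holds for responders who stop later without progression and are not in complete response.

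**Working it through.** **Step 1. Follow each type of patient through the text.**

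| Patient | Trigger in 2.4 | Other scheduled imaging |
|---|---|---|
| Stops doxorubicin after 1 or 2 doses, stays on pembrolizumab | None met | Only the cycle columns of 6.1, if read as applying |
| Stops doxorubicin after 3 to 5 doses, stays on pembrolizumab | First met; second and third never met | As above |
| Stops all treatment before the first scan | None met | None dated: 6.1 blank, 5.6 without an interval |
| Stops all treatment later, no progression, not in complete response | No later trigger met | None dated: as above |
| Off treatment in complete response | 12-weekly | Not needed |

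Between the 30-day visit and survival follow-up, which is by telephone and starts at confirmed progression or new therapy, a patient not in complete response has no dated assessment. The cycle positions of the on-treatment marks in 6.1 are not relied on here, because the table may have shifted when it was read from PDF.

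**Step 2. Reproduce the design.** Inputs from 8.2: n1 = 20, continue at 2 or more; n2 = 15, success at 10 or more.

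P(success | p) = sum over x = 2 to 20 of P(X1 = x) × P(X2 ≥ 10 − x), with X1 ~ Bin(20, p) and X2 ~ Bin(15, p).

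- p = 0.15: 0.029, within the stated 0.05.
- p = 0.35: 0.835, close to the stated 85%.

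**Step 3. Unscanned patients replaced (natural reading of 5.7).** Let u be the share of treated patients who stop unscanned. The documents give no value, so u is an assumption. Suppose all are true non-responders and the true ORR among all treated is 15%. The rate among the 35 evaluable patients is then 0.15 / (1 − u), which goes into the formula above. The number treated is 35 / (1 − u).

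| u | Treated | Rate among evaluable | P(10 or more responses) |
|---|---|---|---|
| 0% | 35 | 15.0% | 0.029 |
| 5% | 36.8 | 0.15/0.95 = 15.8% | 0.040 |
| 10% | 38.9 | 0.15/0.90 = 16.7% | 0.055 |
| 15% | 41.2 | 0.15/0.85 = 17.6% | 0.076 |

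These rows correspond to about 2, 4 and 6 replaced patients. The stated 0.05 is passed somewhere between 5% and 10%.

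**Step 4. Unscanned patients counted as non-responders instead.** Remove k patients from the 35 as certain non-responders, keep the same rules, and set p = 0.35 for the rest.

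| k of 35 | 0 | 1 | 2 | 3 | 4 |
|---|---|---|---|---|---|
| P(success) | 83.5% | 80.4% | 77.0% | 73.1% | 68.9% |

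How the k patients split between the stages changes the result by less than 0.1 percentage point. The loss is an upper bound: it assumes early stoppers would have responded at 35% had they been scanned. If they are already the non-responders within a true 35%, there is no loss.

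**The case against.** The strongest reply is that the plan does cover these patients. Section 5.6 requires disease-status follow-up until progression, 7.1.2.6 sets the imaging method, and RECIST 1.1 sets the criteria. That stands. A reader might infer that early stoppers are not followed at all, and the documents do not support it. What is missing is the interval for patients not in complete response, together with the section that should have described the follow-up period.

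Second, a patient on pembrolizumab alone still passes through the numbered cycles of 6.1, and the footnote shows that scanning does not move with treatment delays. This also stands in part: it cannot be said that such a patient would never be scanned. But 2.4 and 6.1 then give different answers, and neither point helps a patient who has stopped both drugs.

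Third, a reader might infer that the main harm is lost power. That assumes unscanned patients count as failures, whereas 5.7 points to replacement. Step 4 is therefore the alternative case. The main risk to ORR runs upward.

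Fourth, 5.2.1.3 might be cited as creating unscanned patients, because it lets some stay on pembrolizumab after leaving doxorubicin. It does not show this: the rule concerns patients already responding who come off after two dose reductions.

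Finally, a patient with no scan has no documented response and so does not enter duration of response. That endpoint is affected only through responders who stop later.

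**Conclusion.** The point holds as a gap in the assessment schedule. Followed as written, response and progression assessment depends on tolerating treatment, and a patient who stops everything before the first scan has no dated response assessment.

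The consequence for ORR is conditional. With replacement, false-positive risk rises from 0.029 to 0.040, 0.055 or 0.076 at 5%, 10% or 15% unscanned. This assumes that those patients are true non-responders, that 5.7 treats them as not evaluable (it does not define the term), and that the 15% null is a rate among all treated patients. Nothing in the documents says how many patients will stop early, so it cannot be claimed that ORR will be biased, only that the plan permits it. For PFS, neither direction nor size can be stated: late detection lengthens it, while imaging prompted by symptoms could bring a progression date forward.

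The plan should be changed on this point. The gap is inexpensive to close and bears on the phase II primary endpoint.

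**What to change.** 1. In 2.4 and 6.1, set every scan in weeks from cycle 1 day 1, regardless of how many doxorubicin doses were given. With pembrolizumab alone in cycle 1 and on-time 3-weekly dosing, doxorubicin doses 1 to 6 fall at weeks 3, 6, 9, 12, 15 and 18. The first scan in 2.4 is then due by week 12 and the second at weeks 21 to 24 (18 + 3 to 18 + 6), so a calendar can be written without moving the scans of patients treated on time.
2. State that the same calendar continues after either or both drugs stop, at the 12-week (± 1 week) interval 2.4 already uses, until progression or new anti-cancer therapy. A separate scan at discontinuation is then not needed.
3. Replace the reference to 7.1.5.4 in 7.1.4.1 with this rule.
4. In 5.7, state that a treated patient who stops early without a post-baseline scan counts as a non-responder in the primary ORR and is not replaced.

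**Cost.** Protocol wording and a flow-chart revision; a few off-treatment scans within follow-up that 5.6 already requires; and a slightly less favourable ORR. Any power loss under item 4 is bounded by Step 4 and applies only to patients who remain unscanned once the calendar continues after stopping.

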2.5 Phase I dose Escalation of Doxorubicin

A dose limiting toxicity (DLT) will be defined as a possibly-related, unexpected SAE of grade 3 or higher or any adverse event at least possibly related to either agent requiring discontinuation of either drug. The DLT monitoring period will be six weeks (2 cycles) after the patient receives both Doxorubicin and Pembrolizumab.

The Phase I dose escalation will use a “3+3” phase I trial design. All patients will receive a flat dose of 200 mg Pembrolizumab every 3 weeks. Patients will have “priming” with a dose of single agent Pembrolizumab before receiving the combination of Pembrolizumab with doxorubicin. Three patients will be treated at the 45mg/m² dose of doxorubicin. Although this is lower and has considerably less toxicity than the standard of care dosing of 75 mg/m², this dose has clinical activity and is still within the range of acceptable dosing, particularly for sarcoma patients with poor performance status or comorbidities (O'Bryan, Baker et al. 1977). In order to prevent accumulation of unexpected serious adverse events (SAEs), the second patient will not start treatment with Pembrolizumab until 10 days after the first patient has received the combination of Pembrolizumab with doxorubicin. Patients will be monitored for adverse events that might be study related until their last study related visit 30 days after discontinuation of therapy. If the first patient develops a DLT, a data safety monitor board (DSMB) will meet before the second patient is treated in order to discuss the toxicity and make recommendations regarding trial modifications.

If at least one of the first three patients develops DLT, a total of six patients will be treated at this dose level. If two patients develop DLT at the 45mg/m² dose level, the trial will immediately stop accrual and a data safety monitoring board (DSMB) will meet to discuss whether to modify, stop or continue the trial.

Dose escalation to the 75 mg/m² dose of doxorubicin will be contingent upon acceptable safety data following the combination of Pembrolizumab and doxorubicin at the 45 mg/m² dosing. If only one of the six patients develops a DLT, a DSMB will meet prior to dose escalation to review the specific nature of the toxicity and determine if any protocol modifications are necessary prior to proceeding with the dose escalation. If there is no DLT among the first three patients, the trial may proceed immediately to the 75 mg/m² once the third patient receives cycle three (the second cycle including both Pembrolizumab and doxorubicin) without DSMB review.

As was done in the previous cohort, the second patient at the 75 mg/m² dose will not start treatment until 10 days after the first patient has received the combination of Pembrolizumab and doxorubicin at the 75 mg/m² dose level. If the first patient treated has a DLT, a DSMB will meet prior to treatment of the second patient. If two of the first six patients treated using 75 mg/m² doxorubicin develop a DLT, the phase II extension will occur using the 45 mg/m² dosing. The DSMB will meet prior to the phase II expansion. After this, the DSMB will continue to meet at least every six months while the study is enrolling.

[figure not shown]
During the dose escalation period of the trial (up to the first six patients at each dose level), patients will be monitored for 4 hours in the clinical trials unit after receiving their first infusion with the drug combination; monitoring is not required for the Cycle 1 dose of single agent pembrolizumab. After this first combination dose, patients may leave the infusion center immediately after receiving their infusions.

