8.2 Statistical Analysis Plan

Phase I Design:

The primary objective of the phase I component of this study is to evaluate the safety of Pembrolizumab given in combination with Doxorubicin among patients with advanced soft tissue sarcoma. The phase I component of this study will use a 3+3 design to evaluate the 45 mg/m² and 75 mg/m² Doxorubicin dosing in combination with Pembrolizumab. Dose-limited toxicities will be evaluated through the end of the first cycle combining Pembrolizumab with Doxorubicin.

The study design is as follows:

- Initially enroll 3 patients into the 45 mg/m² cohort
 - If 2 of 3 experience a DLT, stop and conclude that Pembrolizumab may not be given safely with Doxorubicin at the protocol-specified dose levels.
 - If 1 of 3 patients experiences a DLT, enroll 3 more patients.
 - If less than 2 of 6 experiences a DLT then initiate enrollment to the 75 mg/m² cohort.
 - If 2 or more experience a DLT, stop and conclude that Pembrolizumab may not be given safely with Doxorubicin at the protocol-specified dose levels. Should this occur, discussions will initiate with the DSMB and Merck about whether the protocol could be altered to make the regimen safe or whether the study should be halted.
 - If 0 of 3 patients experience a DLT then initiate enrollment to the 75 mg/m² cohort
- If 45 mg/m² is determined safe, enroll 3 patients into the 75 mg/m² cohort
 - If 2 of 3 experience a DLT stop and conclude that the MTD is 45 mg/m²
 - If less than 2 of 3 patients experience a DLT, enroll 3 more patients.
 - If less than 2 of 6 experience a DLT then conclude 75 mg/m² is the MTD
 - If 2 or more experience a DLT, stop and conclude that that the MTD is 45 mg/m²

The maximum sample size for the phase I component is 12 patients.

Phase II Design:

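### Sections 2.5 and 8.2 set different DLT windows (two combination cycles against one), so the same toxicity data at 75 mg/m² can give opposite phase II doses

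*Combined protocol and SAP*

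**What the plan says.** Section 2.5 fixes the observation period for dose-limiting toxicity: "The DLT monitoring period will be six weeks (2 cycles) after the patient receives both Doxorubicin and Pembrolizumab". The Phase I Design part of Section 8.2 gives a different one: "toxicities will be evaluated through the end of the first cycle combining Pembrolizumab with Doxorubicin".

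The decision threshold at 75 mg/m² is the same in both places. Under Section 2.5, if two of the first six patients "develop a DLT, the phase II extension will occur using the 45 mg/m² dosing". Under Section 8.2, two or more makes 45 mg/m² the MTD, and otherwise: "If less than 2 of 6 experience a DLT then conclude 75 mg/m² is the MTD". Section 2.1 makes 75 mg/m² the default phase II dose.

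With no DLT in the first three patients at 45 mg/m², Section 2.5 lets escalation proceed "once the third patient receives cycle three (the second cycle including both Pembrolizumab and doxorubicin) without DSMB review". It also staggers the higher cohort: "the second patient at the 75 mg/m² dose will not start treatment until 10 days after the first patient has received the combination". Before the expansion there is a review: "The DSMB will meet prior to the phase II expansion".

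**The concern.** The two windows cannot be reconciled by choosing a different starting point. Six weeks counted from the pembrolizumab priming dose would end with the first combination cycle, but Section 2.5 counts from receipt of both drugs. Its window therefore covers cycles 2 and 3, and Section 8.2 covers cycle 2 alone. Section 5.2 repeats the DLT definition without a window. The diagrams in Sections 2.5 and 2.7 could not be read in the text available; nothing else says which section prevails.

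Events in the second combination cycle are plausible on the protocol's own account. Section 5.2.1.2 says immune-related events can appear soon after the first dose or months after the last. Table 3 requires permanent discontinuation of pembrolizumab for several of them, and a possibly related event that forces discontinuation of either drug is a DLT.

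Safety is the primary objective of phase I, and this count selects the doxorubicin dose for up to 35 phase II patients. A rule that returns two answers for the same data leaves the dose to be argued after the data are known.

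**Working it through.** **The plan's own figure.** Section 8.2 gives a phase I maximum of 12 patients. Six at 45 mg/m² plus six at 75 mg/m² is 12, so the figure reproduces. It does not depend on the window.

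**Decision by pattern.** Let *a* be the number of the six patients at 75 mg/m² with a DLT in the first combination cycle, and *b* the number of other patients whose first DLT comes in the second. Section 8.2 counts *a*; Section 2.5 counts *a* + *b*. Fewer than two gives 75 mg/m²; two or more gives 45 mg/m².

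| a | b | Section 8.2 | Section 2.5 |
|---|---|---|---|
| 0 | 0 or 1 | 75 | 75 |
| 1 | 0 | 75 | 75 |
| 1 | 1 | 75 | **45** |
| 0 | 2 | 75 | **45** |
| 1 | 2 | 75 | **45** |
| 2 | 0, 1 or 2 | 45 | 45 |

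Both rules count patients, so the events must be in different patients. Two DLTs in one patient count once under either window.

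**How often.** The documents give no DLT rate or timing, so these inputs are assumptions. Let p6 be the six-week DLT risk and p3 the first-cycle risk. Each of six patients is early (p3), late (p6 − p3) or neither (1 − p6).

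- P(opposite decisions) = P(Bin(6, p3) ≤ 1) − P(Bin(6, p6) ≤ 1).
- P(exactly one early, one late, no other) = 30 × p3 × (p6 − p3) × (1 − p6)^4.
- Front-loaded case: p3 = 0.8 × p6. Constant hazard: p3 = 1 − (1 − p6)^0.5.

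Stopping after two DLTs in the first three patients does not alter this, because two of three already means at least two of six.

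Worked case, p6 = 0.20. Six-week window: 0.8^6 + 6 × 0.2 × 0.8^5 = 0.2621 + 0.3932 = 0.6554 chance of selecting 75 mg/m². One-cycle window, front-loaded (p3 = 0.16): 0.7528, difference 0.0974. One-cycle window, constant hazard (p3 = 0.1056): 0.8746, difference 0.2192. Exact 1+1 pattern, front-loaded: 30 × 0.16 × 0.04 × 0.8^4 = 0.0786.

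| Assumed six-week risk | 5% | 10% | 20% | 25% | 33% |
|---|---|---|---|---|---|
| Opposite decisions, 80% early | 0.0112 | 0.0370 | 0.0974 | 0.1214 | 0.1433 |
| Opposite decisions, constant hazard | 0.0238 | 0.0799 | 0.2192 | 0.2795 | 0.3430 |
| Exact 1+1, 80% early | 0.0098 | 0.0315 | 0.0786 | 0.0949 | 0.1053 |
| Exact 1+1, constant hazard | 0.0153 | 0.0492 | 0.1225 | 0.1476 | 0.1629 |

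**Timing at escalation.** Day 0 is the third 45 mg/m² patient's first combination dose; a six-week window ends on day 42. Cycle 3 falls on day 21, and a new patient then needs a 21-day priming cycle (Section 2.2), so the first 75 mg/m² doxorubicin dose falls on day 21 + 21 = 42. Using the 3-day allowance in Section 5.2.2 twice, the earliest is 18 + 18 = day 36. The second patient follows at 42 + 10 + 21 = day 73, or 36 + 10 + 18 = day 64 at the earliest. The gap at escalation is therefore minor.

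**The case against.** The strongest reply is that the trial would not sleepwalk into the wrong dose. The DSMB meets before phase II, its charter (Appendix A, section 4) has it review all grade 3 or higher toxicities, and the principal investigator is the named decision-maker. In phase II any DLT-type event triggers a DSMB meeting, and two halt enrollment until it meets (Section 2.6). Priming also helps: if phase II opened about day 21 after the last phase I patient's first combination dose, the first phase II doxorubicin would fall near day 42, when most second-cycle events would be known. All of this stands and reduces the harm. None of it says whether a second-cycle DLT counts toward the two-of-six rule. The DSMB is advisory, and the phase II halt acts only on patients already treated at the chosen dose.

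A second reply is that one cycle was evidently meant. Section 2.3 withholds growth factor in phase I only during the first combination cycle, and the escalation trigger fits a one-cycle window. Both lean that way, but neither excludes later events; if one cycle was intended, the six-week sentence is simply wrong.

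Third, the larger probabilities need both a high DLT risk and constant hazard. The definition is fairly narrow: related, unexpected serious events of grade 3 or higher, or related events forcing discontinuation. That is fair: at 5% to 10% risk the divergence is 1% to 8%.

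For a late DLT at 45 mg/m², Section 2.5 offers partial cover: "If at least one of the first three patients develops DLT, a total of six patients will be treated at this dose level". This rule and the two-DLT stop are not limited to the time before escalation. They do not say whether 75 mg/m² dosing pauses after a single late event.

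**Conclusion.** The concern holds, and the text must be corrected. Sections 2.5 and 8.2 give incompatible windows with one shared threshold, and three patterns at 75 mg/m² (1+1, 0+2 and 1+2 in different patients) lead to opposite doses. That conclusion rests on the wording alone. The frequency rests on assumed rates and timing: 1% to 14% if DLTs are front-loaded, 2% to 34% under constant hazard, the latter being the high end and the effect small at low risk. The finding does not say which window is the right one.

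**What to change.** Before data accrue, state one DLT window in identical terms in Sections 2.5 and 8.2. Declare the MTD and open phase II only after all 75 mg/m² patients counted in the rule have completed that window.

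- **If six weeks is kept:** give the first 75 mg/m² doxorubicin dose only once the 45 mg/m² cohort has completed the window; priming may start earlier. State whether 75 mg/m² dosing pauses after a single late DLT at 45 mg/m².
- **If one cycle is kept:** correct the six-week sentence in Section 2.5. The escalation trigger already fits.

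The cost is protocol and SAP wording. Keeping six weeks adds at most about three weeks before phase II opens, and little or nothing at escalation because of the priming cycle. Keeping one cycle adds no wait.
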